### CONTROL:

- v. Those randomized to the Control group (The AROMA INHALER from Control group packets is labeled with participants ID# and kept in a secure location until they complete the study. It will have been opened and demonstrated with the participant during study introduction)
  1. Left pocket (in this order)
    - a. Welcome letter
    - b. Copy of consent
  2. Right pocket (in this order)
    - a. Logbook (with dates written in)
    - b. Reminder paper
  3. Postage paid envelope (with date and instructions for return on note attached to front of the envelope)

## How Participants are Returning Study Materials:

Postage paid envelop is marked "Complete the Logbook and the surveys and return them ALL on \_\_\_\_\_. " Add date they will complete the 7-day study

- e. (e.g., If they received their packet and instructions on October 11, then they should begin their study on the NEXT FULL DAY, October 12, and their study would be complete on October 19. October 19 is the date entered on the note attached to this envelope)

## Timing Of Gift Card

Once the final survey is received, the \$20 gift card will be issued to the intervention group and the \$20 gift card and inhaler to the control group.

## Frequently Asked Questions:

### What if a Participant Loses Their Aroma Inhaler?

Participants are instructed to contact [name] at [[contact]](mailto:[contact]) if they lose their inhaler and arrange for a replacement.

- The study will continue during the time they are without an inhaler and resume when they have one.
- The researcher will note this occurrence, but data analysis will occur as if the days were consecutive.

### What if a Participant has a Reaction?

Participants are instructed to contact [name] at [[contact]](mailto:[contact]) if they experience adverse reactions such as a headache.

- They are asked to stop using the inhaler, recap it, and retry the inhaler as directed a little later.
- If unpleasant effects, such as headache continue, discontinue use, and contact [name], Investigator at [[contact]](mailto:[contact])
- If participant feels any severe reaction like difficulty breathing, they are asked to seek medical care

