## Research Summary

### Updates to Study Protocol

Update: IRB amendment 09262022 (Appendix G)

To allow Stages one, two, and three and peer recovery persons to participate.

Update: IRB Amendment 08312022 (Appendix H)

To recruit and consent participants online

Update: From QIP Audit 10252022 (Appendix I)

Annual Review with approval received 7/29/2023

8/23/2023 Per email communication with co-I [name], BMed no longer using site approval forms. I have approval to proceed with recruitment when IRB approval is obtained.

Update to consent process 8/2023 (completed)

Communication with participants, begin using RedCap WVU for all surveys and emails. WVU phone and computer for all communication.

10/23/2023 Update: Will no longer include copy of consent in study packets mailed to participants. This will save on mailing costs. Participants can download and print or save to their devices. Approved 11/7/2023

11/21/23 Submitted amendment re: addition of [name] and [name] CITI training certificates to the protocol

12/27/23 Amendment to add a population from Health Right, approved 2/5/2024

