## Safety Monitoring & Unanticipated Event Reporting

This study involves use of an aroma inhaler. This study is only minimal risk because it involves aroma of a citrus essential oil named Bergamot. This essential oil is impregnated on a pure cotton wick within a manufacturer-sealed aroma inhaler. Participants are instructed and will demonstrate back to the researcher that they will use the inhaler in the prescribed fashion.

Participants encounter odors and aromas during daily life and the anticipated magnitude of harm or discomfort anticipated in the research is not greater in and of itself than those ordinarily encountered in daily life or during the performance of routine physical or psychological examinations or tests.

Participants will have an informational session with a Registered Aromatherapist, [name], who will demonstrate use and care of the aroma inhaler.

The following reminder is provided in writing for participants.

\*(When not in use, recap to close & store in a cool, dry place away from children and pets) It is OKAY to keep your closed inhaler in your pocket or purse and at room temperature ☺  
Do not tamper with the packaging. Keep out of reach of children and animals. If you develop any adverse reactions such as a headache, stop, recap inhaler, and retry a little later. If unpleasant effects, such as headache continue, discontinue use and contact [name], Co-Investigator at [[contact]](mailto:[contact])

Every effort has been made to ensure the safety of all Participants and those at the study site.

1. Aroma inhalers are factory sealed
2. Tamper resistant packaging is used
3. Safety data sheets are available online and on site
4. Inhalation of essential oils such as Bergamot is considered low risk
5. Specific instructions are provided
6. A Registered Aromatherapist created and manages this study

Participants will be instructed to seek medical care if needed and are able to withdraw from the study at any time without any repercussions. Participants are already in the care of medical staff.

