**Follow these steps to use your Logbook:**

**Use your logbook to track how you are using your aroma inhaler and how you are feeling**

1. Use a new page of the logbook for each of the seven days of the study
2. If you forget or purposely do not do the aroma inhaler, please make a note with a brief reason why
3. Do not stop the study because you miss a step of using the inhaler or recording in the logbook
4. Keep your logbook in a secure place as we will collect it at the end of the study
5. Do not write important or private information that does not have to do with using your aroma inhaler in this logbook
6. Do not write your name on the logbook
7. All information provided in the logbook will be kept confidential
8. **Return within 3 days of completion**

**\*NOTE:** If you develop any uncomfortable symptoms such as a headache, stop using the aroma inhaler, recap, and retry a little later. If unpleasant symptoms continue the next time, discontinue use and contact [name], the Principal Investigator (PI), at [[contact]](mailto:[contact]).

Day 1

Please indicate each time you use your inhaler today (approximate time of day)

- I used my aroma inhaler as directed for the first time today
- I used my aroma inhaler as directed for the second time today
- I used my aroma inhaler as directed for the third time today

Any additional comments:

If you used your aroma inhaler any extra times, please indicate when and brief reason why  
(example: 2:30p, feeling stressed, and it seemed to help)

One time at the end of each day, after using the inhaler throughout your day, place an X on the line under "I feel as comfortable as possible today"

I feel as comfortable as possible today

Strongly disagree	Strongly agree
<hr/>	

Comments:

If you have any questions or comments, contact [name] at [[contact]](mailto:[contact]).  
Thank you

Day 2

Please place a check mark or X on the line each time you use your inhaler today

- I used my aroma inhaler as directed for the first time today
- I used my aroma inhaler as directed for the second time today
- I used my aroma inhaler as directed for the third time today

Comments: (example: I used my aroma inhaler an extra time today because...)

One time each day place an X on the line under "I feel as comfortable as possible today"

I feel as comfortable as possible today

Strongly disagree	Strongly agree
<hr/>	

Comments:

If you have any questions or comments, contact [name] at [[contact]](mailto:[contact]).

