- Receive a \$20 gift card
- You will receive the aroma inhaler and all other study materials as our way of saying thank you!

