## Appendix E

### Reminder Paper

#### SEVEN DAY AROMA INHALER STUDY

(Please post this in a place where you will see it each day as a reminder to use your aroma inhaler and logbook) **Thank you for your participation ☺**

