###### 3. Recap Inhaler & Record all uses & reactions to the inhaler in the Logbook\*\*

###### 4. Keep your aroma inhaler and logbook in a safe place. The aroma inhaler is yours to keep.

\*\*The logbook is returned at the end of this study

\*(When not in use, recap to close & store in a cool, dry place away from children and pets) It is OKAY to keep your closed inhaler in your pocket or purse and at room temperature ☺

Do not tamper with the packaging. Keep out of reach of children and animals. If you develop any adverse reactions such as a headache, stop, recap inhaler, and retry a little later. If

OFFICE OF HUMAN RESEARCH PROTECTION

unpleasant effects, such as headache continue, discontinue use and contact [name],

Investigator at [[contact]](mailto:[contact])

Thank you!

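### The posted Reminder paper and the intervention logbook note leave out the protocol's instruction to seek medical care for a severe reaction, and the Reminder paper advises retrying after any adverse reaction

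*Combined protocol and SAP*

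**What the plan says.** Under the frequently asked question on reactions, the protocol sets out three steps. A participant with an effect such as headache stops, recaps the inhaler and tries again later. If the effect continues, the participant discontinues and contacts the investigator. The third step covers serious events: "If participant feels any severe reaction like difficulty breathing, they are asked to seek medical care".

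Two participant sheets give reaction advice:

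- The Reminder paper (Appendix E) says: "If you develop any adverse reactions such as a headache, stop, recap inhaler, and retry a little later". It then says to discontinue and contact the investigator if unpleasant effects go on. Participants are told: "Please post this in a place where you will see it each day as a reminder to use your aroma inhaler and logbook".
- The intervention logbook note (Appendix D) says: "If you develop any uncomfortable symptoms such as a headache, stop using the aroma inhaler, recap, and retry a little later". It ends in the same way, with discontinuation and contact.

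The section on safety monitoring and unanticipated event reporting reproduces the Reminder wording, introduced by "The following reminder is provided in writing for participants". Later in that section a separate sentence says "Participants will be instructed to seek medical care if needed", without naming the sheet or conversation that delivers the instruction.

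**The concern.** The investigators judged that a severe reaction needs its own response and wrote one. The sheets that participants have at home stop before reaching it.

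The inhaler is used without supervision, at least three times a day for seven days and additionally as needed. If a participant reacts badly, the sheet most likely to be in view is the posted Reminder paper. For a participant short of breath, its first advice after stopping is re-exposure, and its second is to contact the investigator. The protocol would have sent that participant to medical care.

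This is a question of participant safety. It does not touch power, endpoints or analysis.

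**Working it through.** No formula applies. The check is a comparison of texts and a count of who receives which sheet.

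**Step 1. Compare the instructions.**

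| Source | What triggers the retry advice | If effects continue | Severe reaction |
|---|---|---|---|
| Protocol FAQ on reactions | Adverse reactions, headache as example | Discontinue, contact investigator | Seek medical care |
| Reminder paper (Appendix E) | *Any* adverse reactions, headache as example | Discontinue, contact investigator | Not mentioned |
| Intervention logbook note (Appendix D) | Any uncomfortable symptoms, headache as example | Discontinue, contact investigator | Not mentioned |
| Safety section, copy of the reminder | Same as Reminder paper | Same as Reminder paper | Not in the copy; a general promise appears separately |

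The first two steps agree throughout, so this is an omission and not a conflict. The severe-reaction step appears on 0 of the 2 sheets.

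**Step 2. Check that the omission is real.** The Reminder paper runs to its closing thanks, and the logbook note gives both of its steps before Day 1 begins. Neither gap looks like the result of removed pages.

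**Step 3. Read the wording.** In the protocol FAQ, the severe-reaction line limits the retry advice. On the Reminder paper that limit is absent, and the trigger covers any adverse reaction. Headache is given as an example and does not narrow it. The logbook trigger is milder in tone, but it has no severe step either.

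**Step 4. Count recipients.** The Sample Size section plans 49 intervention and 49 control participants: 49 + 49 = 98. The packet lists for both arms include the Reminder paper, so the planned number of recipients is 98.

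- The 49 intervention participants have both sheets during the week. They return the logbook at the end and keep the inhaler.
- The 49 controls are given the inhaler after the final survey arrives. Their logbook has no reaction note and closes with "You will receive the aroma inhaler and all other study materials as our way of saying thank you". Of the two sheets, they have only the Reminder paper.

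These figures count who holds the sheet. They are not an estimate of harm.

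**The case against.** The strongest reply is that the plan already commits to the instruction. The FAQ states it, the safety section promises it, participants attend an information session with a Registered Aromatherapist, and they are already under medical care. The cover letter and the consent form were not available for review, and the contents list shows that the consent has a section on risks and discomforts, where such an instruction would naturally sit. On this view the point is only about which sheets should repeat it.

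Much of this stands. It cannot be claimed that no participant document contains the step. But the consent is now less likely to be at hand: "Will no longer include copy of consent in study packets mailed to participants". Participants can still download or save it. Oral advice, or a line in the consent, would also leave the posted sheet telling people to retry after any adverse reaction.

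A second reply is that, in context, the Reminder paper plainly means mild effects like headache, which matches the risks named in the Risk section, and that its first command is to stop. That is a reasonable reading, and probably the intended one. A safety sheet should not depend on it when the protocol spells out the exception elsewhere.

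A third reply is that risk is low and controls have no home supply of the inhaler during the study week. Asthma, other serious respiratory disease and citrus allergy are exclusions, and reactions to a screening sniff are recorded. This stands and limits the size of the point. Even so, screening cannot rule out a first or unrecognised reaction, and the amendment letter in Appendix G moved the initial sniff to the participant's home.

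**Conclusion.** The point holds. The Reminder paper and the intervention logbook note both omit the protocol's own step for a severe reaction, and the Reminder paper attaches its retry advice to any adverse reaction. Followed literally, the posted sheet gives worse advice than the protocol.

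It is a low-probability gap in safety wording that should be corrected. The sheet reaches 98 planned participants, of whom 49 are to use the inhaler at home during the study week. The documents give no reaction rate, so expected harm cannot be estimated. Confidence is medium, because the cover letter and consent may carry the instruction and it may also be given orally. Either would reduce the practical consequence but would leave the two sheets as they are.

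**What to change.** On the Reminder paper, on its copy in the safety section and in the intervention logbook note:

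1. Limit the retry advice to mild effects. For example: *If you notice a mild effect such as a headache, stop, recap the inhaler and try again later. If it continues, stop using the inhaler and contact the investigator.*
2. Add the severe step. For example: *For a severe reaction, such as trouble breathing, stop using the inhaler, do not retry, and get medical care.*

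Because the Reminder paper goes to both arms, correcting it also covers controls when they receive the inhaler. The cost is a reprint of two sheets and a minor IRB amendment. Data collection, sample size and analysis do not change.

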### What if a Participant Wants to Withdraw from the Study?

Participants are instructed to contact [name] at [[contact]](mailto:[contact]) if they wish to withdraw from the study.

- They are free to withdraw from the study at any time without penalty
- They can keep the aroma inhaler and all study materials
- They are asked to return the logbook if they completed it
- They will not receive the \$20 gift card

## Appendix A

### PRESCREEN SURVEY

#### To be completed by the Enroller:

1. Please answer the following questions about aversion (dislike) or allergy.
  - a. Do you have a strong aversion to smells of citrus and/or citrus fruit(s) themselves (such as grapefruit, orange, lemon, or bergamot). Yes/No (If no, please go to the next question)
    - i. Do you have any allergies to citrus? Yes/No (If no, answer next question)
    - ii. This study uses the pure essential oil of Bergamot. Have you ever smelled this fruit or essential oil? Yes/No
    - iii. If yes, you have smelled Bergamot fruit or essential oil, do you dislike the smell? Yes/No
    - iv. If yes, you dislike the smell of Bergamot essential oil, you are excused from participation in this study.

If yes, you have a strong dislike or allergy to Bergamot fruit or essential oil, you are not eligible to participate in this study.

If no strong aversion or allergy to Bergamot, proceed with the following questions.

2. Do you or have you ever been told by a doctor that you have any of the following medical or health conditions? Yes/No (If No, go to question 3)
  - a.  Severe breathing problems such as asthma, chronic bronchitis, or a chronic obstructive pulmonary disease (COPD)
  - b.  Pregnant or the possibility of becoming pregnant and/or breastfeeding
  - c.  Allergies to citrus fruits such as grapefruit, lemon, orange, or bergamot

If yes to any responses to question 2, you are not eligible to participate in this study.

3. Have you ever tried any integrative or complementary therapies (examples include; massage, yoga, acupuncture, aromatherapy with essential oils, herbs, meditation, mindfulness practices etc.) Yes/No (If Yes, please answer the following. If No, go to question 5)
  - a. If yes, list which ones? \_\_\_\_\_
  - b. If yes, what was your main reason for using complementary therapies? Choose all that apply
    - i.  Pain
    - ii.  Anxiety
    - iii.  Relaxation
    - iv.  Stress relief

v. Other, please write in \_\_\_\_\_

c. If there is a specific therapy used for a specific symptom, please write the therapy beside the symptom listed above.

d. On a scale of 0 to 10 with 0 being not at all effective and 10 being very effective, how effective was the therapy noted above for relief of the symptom? (Example: Pain, massage, 7/10)

4. Was one of the complementary therapies you have tried aromatherapy or essential oils? Yes/No (If Yes, please answer the following. If No, go to question 5)

- No, I have not used aromatherapy or essential oils. (Proceed to question 5)
- Yes, I have used essential oils and have tried (please list the essential oils you have tried) \_\_\_\_\_
- Of those essential oils you have tried, which one or ones would you consider to be your favorite(s) \_\_\_\_\_
- Of those essential oils you have tried, which one or ones would you consider to be your least favorite(s) \_\_\_\_\_
- Have you ever tried Bergamot essential oil? Yes/ No
  - If yes, why did you try it? \_\_\_\_\_  
If yes, what, if any effect, did you think it had? \_\_\_\_\_

5. Do you have difficulty smelling or recognizing odors? Yes/No

- If yes, do you think your problems with smelling are because of allergies or stuffy nose and congested sinuses? Yes/No
  - Are you currently feeling sick with a cold, the flu, or with COVID? Yes/No
- If yes, you have problems with your sense of smell, have you ever been *told by a doctor* that you have a problem with your sense of smell? Yes/No
  - If yes, have you ever been diagnosed or told by a doctor that you have *anosmia*, which is a total loss of the sense of smell? Yes/No
    - Was this loss of smell related to COVID or some other illness? Yes/No

If yes, approximately when did the loss of smell begin \_\_\_\_\_

END OF SURVEY

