## Study Population

Adults (>18 years) who are currently receiving treatment for SUD in the outpatient treatment program at West Virginia University Chestnut Ridge Center (WVUCRC) (n = 340 approx.).

Inclusion criteria are patients diagnosed with SUD who have completed intensive acute phase 1 treatment, and who desire to pursue continuous recovery phases (per facility protocol). All participants must be alert and oriented, provide written consent, and be able to read and write English.

[figure not shown]
Exclusion criteria are patients diagnosed with severe mental illness (who cannot consent to participate), have a medical history of asthma or other serious respiratory disease, and known allergy to citrus. There are no exclusion criteria for gender, race, and/or ethnicity.

Anyone who meets inclusion criteria in the sample population is invited to participate. I am advertising throughout entire population of the study.

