### **Plus, the following**

#### **Data will be collected from the chart and from survey (self-report)**

1. Identifier variables of Comfort, Ease, and Stress
2. Stage of treatment in the SUD treatment program (Chart)
3. Presence of anxiety and/or depression (Chart)
4. Presence of severe mental illness Dx (Chart)
5. Allergies to citrus fruits such as grapefruit, lemon, orange, or bergamot (Chart and self report)

6. Previous experience with any integrative or complementary therapies such as yoga, massage, acupuncture, aromatherapy with essential oils, herbal preparations, meditation, mindfulness practices (Self-report)
7. Pregnant and/or nursing (Self-report)
8. Severe breathing problems such as asthma, chronic bronchitis, or COPD (Chart and self-report)
9. Report of sense of smell (self-report)
10. Dx of a problem with sense of smell (Chart and self-report)
11. Current illness with cold, flu, or covid (Self-report)

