## Prior to opening a Study Packet

1. In a private location, Enroller will determine eligibility for this study.
  - a. Inclusion criteria are as follows:
    - i. Older than 18 years of age
    - ii. Currently enrolled in treatment
    - iii. Have completed intensive phase 1 and wish to continue with treatment
    - iv. Alert & oriented
    - v. Able to provide written consent
    - vi. Able to read & write English
  - b. Exclusion criteria are as follows:
    - i. Diagnosed with severe mental illness
    - ii. Medical history of asthma
    - iii. Other serious respiratory disease
    - iv. Known allergy to citrus
2. In a private location, Enroller will prescreen using created survey tool (appendix A)
  - a. Use the prescreening survey provided
  - b. Read prescreening survey to participants and record answers
  - c. If not contraindicated by prescreening questions, allow participant to smell the aroma inhaler (3 inches from nose)
    - i. Record all reactions, “liked the smell”, “sneezed”, “said ‘yuck’” on the presurvey. Record “no negative reactions” as applicable (This is a vital component of aromatic research)
3. IF PARTICIPANT IS INELIGIBLE, thank them for their time, note on MLS that they were screened and why they were ineligible. Use the special section at the end of the MLS to make this notation. Do not use an Id # space. Write “ineligible” and the date across the top of the survey.
4. IF PARTICIPANT IS ELIGIBLE, file prescreening form in predetermined place and obtain a study packet in the order they are arranged (001-098)
  - a. Enter date and name of participant on the **Random Number Table (RNT)** sheet
5. Record Unique Identifier packet number on **Master Log Sheet (MLS)**
  - a. Use MLS to track Participants
  - b. This Unique Identifier number is already on every document in each packet

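### The criteria exclude any history of asthma, but the prescreen and chart items name asthma only as an example of a severe breathing problem

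*Combined protocol and SAP*

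**What the plan says.** The criterion appears twice. Study Population excludes people who "have a medical history of asthma or other serious respiratory disease". The list under Prior to opening a Study Packet gives "Medical history of asthma" as exclusion ii, and other serious respiratory disease as a separate exclusion iii. Neither place limits asthma by severity or by date.

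The form that the Enroller reads aloud is the Prescreen Survey in Appendix A. The stem of question 2 is "Do you or have you ever been told by a doctor that you have any of the following medical or health conditions", and its first option, 2a, is "Severe breathing problems such as asthma, chronic bronchitis, or a chronic obstructive pulmonary disease (COPD". A yes to any option makes the person ineligible; a no leads to question 3. The ineligibility check at the end of the form points back to question 2.

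The list of data to be collected, in the Informed Consent Process section, has as item 8 "Severe breathing problems such as asthma, chronic bronchitis, or COPD (Chart and self-report".

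On sequence, step 1 under Prior to opening a Study Packet reads "In a private location, Enroller will determine eligibility for this study". Step 2 is the survey, followed by a test sniff if the answers raise no contraindication. Consent is signed at step 7.

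**The concern.** A criterion protects participants only as far as the questions used to apply it. Here the rule turns on whether a person has ever had asthma, while the form can be heard as asking whether they have a severe breathing problem. Two honest people with the same mild, controlled asthma could answer differently, and only one would be excluded.

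The stake is participant safety. The protocol itself foresees a breathing reaction: "If participant feels any severe reaction like difficulty breathing, they are asked to seek medical care". Participants in the intervention group use the inhaler at least three times a day for seven days. Controls are exposed as well, since the inhaler is opened and demonstrated with them and given to them after the study. The approval letter in Appendix G moves the first sniff to the participant's home, so more depends on the screening questions.

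There is also a record-keeping consequence. Because the form never records asthma separately, a participant enrolled despite a history of it could not be identified from the form afterwards.

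**Working it through.** The plan states no figure on this point, so the check is a comparison of wording.

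| Place | How asthma appears | Severity limit on asthma | Covers past diagnoses |
|---|---|---|---|
| Study Population | History of asthma | None | Yes |
| Prior to opening a Study Packet, exclusion ii | History of asthma, its own item | None | Yes |
| Appendix A, question 2a | Example of a severe breathing problem | Yes, on one reading | Yes, through the stem |
| Data list, item 8 | Example of a severe breathing problem | Yes, on one reading | Not stated |

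Now follow a person with diagnosed asthma that they do not regard as severe.

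1. **Step 1, eligibility determination.** The Enroller has the unqualified criterion in view and would exclude the person if the asthma became known. The step gives no question to ask and no source to consult. The participant-time table lists the survey as the prescreening activity and shows no other screening step.
2. **Question 2a.** If the person takes *severe* as a condition, a truthful answer is no, and the form moves to question 3.
3. **Rest of the form.** No later question mentions asthma, and the closing check only repeats question 2.
4. **Test sniff.** Step 2c makes the sniff depend on the prescreen answers, so it goes ahead.
5. **Chart.** A chart may show the diagnosis whatever the person thinks of its severity. But item 8 carries the same qualifier, so mild asthma need not be recorded under it. Nor is it said when the chart is read. The sniff is at step 2 and consent at step 7, so a chart review done only after consent would come too late for the first exposure.

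**Timing of the diagnosis.** The stem asks about anything a doctor has ever told the person. Childhood or resolved asthma is therefore within the question. It can be missed only in the same way as current asthma, through the word *severe*.

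**Number affected.** An estimate would need p, the share of candidates with a history of asthma; s, the share of those who would answer no to 2a; and c, the share of those caught at step 1 or from the chart. The expected share passing wrongly is p × s × (1 − c). The documents give none of the three, and the result is zero if c = 1.

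**The case against.** The strongest reply is that the narrow reading is only one reading. Item 2a names asthma, and many people with the diagnosis will simply say yes. The Study Population wording, which sets asthma beside *other* serious respiratory disease, itself treats asthma as serious by nature, so the form may be classing it by diagnosis in the same way. The form is also not the only barrier: step 1 applies the unqualified rule, and the chart is a second source. Appendix G mentions a separate data form clarifying what comes from self-report and what from the chart. It cannot be seen here and may be worded better.

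Much of this stands. It turns a certain failure into a possible one. It does not close the gap, because step 1 has no question of its own and the visible chart item repeats the qualifier.

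A reader might draw three stronger conclusions that the documents do not support:

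- **That past asthma slips through on timing.** The stem rules this out.
- **That a given number of the 98 planned participants would be wrongly enrolled.** Any such number would come from outside prevalence and misreading rates, and would usually assume that step 1 and the chart catch nobody.
- **That the stress outcome is compromised because item 4 of the stress survey asks about breathing difficulty.** It is one of 21 items, measured before and after in randomised groups. Wrongly admitted participants would be expected in both arms, so this gives no reason to think the comparison is biased.

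Nor do the documents call the respiratory exclusion the main safeguard. They also provide a test sniff with reactions recorded, a citrus-allergy exclusion, stop-use instructions and direction to medical care.

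**Conclusion.** The inconsistency is real and moderate. The criteria exclude asthma without a severity limit, while the form that controls first exposure, and the chart item meant to support it, can be read as requiring severity. Wrong entry is possible, not certain. It requires that the person take *severe* as a qualifier and that neither the Enroller at step 1 nor the chart brings the asthma to light. The number affected cannot be estimated from the documents. The case for changing the form rests on safety screening and a clear eligibility record, not on the efficacy analysis. It is worth making because the criterion concerns safety and the repair is very cheap.

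**What to change.** - Reconcile Study Population and exclusion ii with question 2a and data item 8, so that all four express one criterion. Which criterion to keep is for the sponsor to decide.
- On the prescreen form, make asthma its own yes/no item, separate from chronic bronchitis, COPD and other breathing problems. If the sponsor adopts a criterion with a limit on severity or timing, the form will need one more line to record it. If the unqualified criterion stays, the single item is enough.
- Use the same asthma item for the chart check, and state whether that check comes before the first sniff.
- Say in step 1 which question or source the Enroller uses to determine each criterion.

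The cost is a few lines on the form and in the enrolment steps. If the unqualified criterion is kept and now asked plainly, slightly more people may fail screening. Neither the sample size nor the analysis changes.
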